6.1 DETERMINATION OF SAMPLE SIZE

This study will enroll approximately 260 patients randomized to either an IV active dose arm or to an IV placebo dose arm in a 1:1 ratio. This sample size provides approximately 80% power to detect a 35% relative reduction in mean ADAS-Cog11 change from baseline when MTAU9937A is compared with placebo assuming an average decline of 6 points for placebo-treated patients, a standard deviation across patients of 7.5, a 10% dropout rate, and a two-sided $\alpha=0.2$ significance level.

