- The study design has been amended to remove Cohort 3. Under protocol Version 4, the protocol allowed for extension of the double-blind treatment period to 73 weeks for those patients who missed more than three doses of blinded study drug because of the COVID-19 pandemic. However, the proportion of patients having missed more than three study drug doses in the double-blind period was not significant; therefore, no patients were enrolled into Cohort 3 (Sections 2.1.1, 2.1.2, 2.1.3, 3.1.1, 3.1.1.1, 3.3.1, 6, 6.2, 6.4.1, and 6.4.2). Appendices 5 and 6 have been removed and subsequent appendices renumbered accordingly.
- Language related to a potential expansion in the study size has been removed. The option to enroll up to 100 additional patients to further mitigate the impact of the COVID-19 pandemic on the study had been incorporated in protocol Version 4. This expansion is now considered unnecessary (Sections 3.1.1, 3.2, 4.1, 6.1, and 9.4).
- Given that no treatment effect was observed on $[^{18}\text{F}]\text{GTP1}$ tau positron emission tomography (PET) in the double-blind treatment period, $[^{18}\text{F}]\text{GTP1}$ PET has been removed during the OLE at Week 145 for Cohort 1, Week 157 for Cohort 2, and at the treatment discontinuation visit (for both cohorts). The provision for optional $[^{18}\text{F}]\text{GTP1}$ tau PET imaging assessments for patients potentially recruited after implementation of protocol Version 4 has also been removed (Section 4.5.8; Appendices 1–4).
- OLE clinical Outcome Assessments (COAs), with the exception of the Columbia-Suicide Severity Rating Scale, have been removed at Week 121 for Cohort 1 and Week 133 for Cohort 2 to reduce patient, caregiver, and site burden. The remaining COA timepoints are considered sufficient to monitor longitudinal progression during the OLE (Appendices 2 and 4).
- Based on the low variability of MTAU9937A pharmacokinetics and the rare occurrence of anti-drug antibodies (ADAs), the collection of serum pharmacokinetic (PK) and ADA samples has been reduced to only once during the OLE, at Week 97 for Cohort 1 and Week 109 for Cohort 2. All other OLE PK and ADA sample collection timepoints have been removed (Appendices 2 and 4).

- The Medical Monitor has been changed; applicable study summary pages and emergency medical contact information (Section 5.4.1) have been updated accordingly.

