2.1 EFFICACY OBJECTIVES

2.1.1 Primary Efficacy Objective

The primary efficacy objective for this study is to evaluate the effects of MTAU9937A compared with placebo on cognition and function on the basis of the following endpoints:

- Change from baseline to the last visit of the double-blind treatment period (Week 49 for Cohort 1 *and* Week 61 for Cohort 2) in cognitive function as measured by the Alzheimer's Disease Assessment Scale, Cognitive Subscale, 11-item version (ADAS-Cog11)
- Change from baseline to the last visit of the double-blind treatment period (Week 49 for Cohort 1 *and* Week 61 for Cohort 2) in functional capacities as measured by the Alzheimer's Disease Cooperative Study—Activities of Daily Living Inventory (ADCS-ADL)

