6.4 EFFICACY ANALYSES

6.4.1 Primary Efficacy Endpoints

The co-primary efficacy endpoints are change in ADAS-Cog11 and ADCS-ADL scores from baseline to the last visit of the double-blind treatment period (Week 49 for Cohort 1 *or* Week 61 for Cohort 2). The difference in mean change from baseline to the last visit of the double-blind treatment period between MTAU9937A- and placebo-treated patients will be estimated using an analysis of covariance model adjusting for *ApoE4* status (*ApoE4+* vs. *ApoE4-*), screening MMSE (16–18 vs. 19–21), baseline [¹⁸F]GTP1 PET standard uptake value ratio, age, baseline ADAS-Cog11 or ADCS-ADL scores, and if appropriate, the number of missed study drug infusions during the double-blind treatment period due to the COVID-19 pandemic. Confidence intervals, as well as least squares estimates, will be used to aid in interpretation of study results.

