6.9 INTERIM ANALYSES

6.9.1 Optional Interim Analysis

Given the hypothesis generating nature of this study, the Sponsor may conduct up to two interim analyses of efficacy. The decision to conduct such an interim analysis and its timing will be documented in the Sponsor's study master file prior to the conduct of the interim analysis. The Clinical Study Report will also document that such an interim analysis occurred. The interim analysis, should it occur, will be performed and interpreted by members of the Sponsor study team and management who would then be unblinded to treatment group (MTAU9937A or placebo).

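### Does sizing the trial on ADAS-Cog11 alone leave the two co-primary endpoints without a sound basis?

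*Combined protocol and SAP*

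**What the plan says.** The primary objective (Section 2.1.1) is "to evaluate the effects of MTAU9937A compared with placebo on cognition and function", with one endpoint for each domain. Section 6.4.1 repeats this: "The co-primary efficacy endpoints are change in ADAS-Cog11 and ADCS-ADL scores from baseline", each taken to the last double-blind visit. The treatment difference on each scale comes from an analysis of covariance. On interpretation, the section says: "Confidence intervals, as well as least squares estimates, will be used to aid in interpretation of study results". It names no hypothesis test, interval level, alpha allocation or success rule.

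Section 6.1, repeated in the synopsis, sizes the trial on one scale: "This sample size provides approximately 80% power to detect a 35% relative reduction in mean ADAS-Cog11 change from baseline", "assuming an average decline of 6 points for placebo-treated patients", with an SD of 7.5, 10% dropout and a two-sided level of 0.2. No ADCS-ADL expected change, SD or target effect appears anywhere. The only ADCS-ADL figure is the 0 to 78 scale range in Section 4.5.7.4.

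Section 6.9.1 describes the setting: "Given the hypothesis generating nature of this study". Section 1.4 calls the study proof-of-concept.

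**The concern.** Calling two endpoints co-primary often means that both must show an effect. On that reading, the chance of meeting the objective cannot exceed the power on either scale, so 80% is a ceiling at the stated inputs. On the opposite reading, where either scale suffices at 0.2, the false-positive rate would rise above 0.2. The protocol chooses neither.

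The missing interval level adds to this. The 0.2 appears only in the sample-size text, so an analyst could report intervals at another level and give a different impression of the same data. A result favourable on one scale only has no reading set down in advance. At stake would be what a positive primary result means.

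**Working it through.** **1. Reproduce the stated power (inputs from Section 6.1).**

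- Difference: 0.35 × 6 = 2.1 points
- Evaluable per arm: 260 × 0.9 / 2 = 117
- Standard error: 7.5 × √(2/117) = 0.981
- Standardised effect: 2.1 / 0.981 = 2.142
- Critical value at two-sided 0.2: 1.282
- Power: Φ(2.142 − 1.282) = Φ(0.860) = 80.5% (80.4% with the t distribution)

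In the other direction, 80% power needs 115 per arm, or 230 in total, and 230 / 0.9 rounds up to 256. The protocol says approximately 260. Both figures agree.

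**2. What the plan yields for interpretation.** At the only level given, 0.2, the matching interval is 80%. Before any gain from covariates, its half-width on ADAS-Cog11 is 1.282 × 0.981 = 1.26 points. Section 6.4.1 produces one such estimate and interval per scale, and each is valid without reference to the other.

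**3. What a both-required rule would imply.** This needs three things the documents do not give: the rule itself, the ADCS-ADL power, and the correlation r between the two test statistics. Joint power is the bivariate normal probability that both statistics exceed 1.282.

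| Assumed ADCS-ADL power | r = 0 | r = 0.3 | r = 0.5 | r = 0.7 | r = 0.9 |
|---|---|---|---|---|---|
| 80.5% (equal) | 64.8% | 67.4% | 69.4% | 71.9% | 75.6% |
| 70% | 56.4% | 59.4% | 61.8% | 64.6% | 68.2% |
| 90% | 72.5% | 74.2% | 75.6% | 77.3% | 79.6% |

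The first cell can be checked by hand: 0.805² = 0.648.

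Suppose instead that 7.5 is an unadjusted SD and the covariates explain 10% to 30% of the variance on both scales. The standard error is then multiplied by √(1 − R²). ADAS-Cog11 power becomes 83.5% to 89.9%, and equal-power joint power runs from 69.8% (R² = 0.1, r = 0) to 86.8% (R² = 0.3, r = 0.9). The answer therefore lies on either side of 80% according to inputs that nobody has stated.

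**4. What an either-sufficient rule would imply.** With 0.2 on each scale, the chance of at least one two-sided false positive is 1 − 0.8² = 36.0% for independent statistics and 26.2% at r = 0.9. Counting the favourable direction only, it is 19.0% and 13.1%, against a nominal 10%. The documents never propose this rule, and the objective joins cognition and function.

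**The case for a change.** The strongest case for a change uses only the sample-size inputs and one outside convention. A reader used to 95% intervals would apply a half-width of 1.960 × 0.981 = 1.92 points. An observed ADAS-Cog11 difference between 1.26 and 1.92 would exclude zero at 80% but not at 95%. At the design effect, a 95% interval excludes zero with probability Φ(2.142 − 1.960) = 57.2%, so the chance of landing in that band is 80.5% − 57.2% = 23%. A sentence fixing the level, and saying whether both scales are required, would remove the doubt at almost no cost.

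The arithmetic is right, and it is true that Section 6.4.1 states neither the level nor the joint reading. But no 95% or 0.05 level appears in the plan, so the contrast is with a convention the sponsor did not adopt. If covariates explain 10% to 30% of the variance, the 23% falls to between 22% and 17%. A report that prints the estimate, its interval and the level lets any reader convert from one level to the other.

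The joint-power table cannot show a shortfall, because the plan claims 80% for ADAS-Cog11 and nothing for the pair. A label in Section 6.1 that the figure is for ADAS-Cog11 would repeat what is there.

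Two further points limit the gain. Section 6.5 mentions a Data Analysis Plan that is not supplied. Its efficacy content is unknown, and it may already hold a rule. Also, the Version 5 amendment rationale reports a double-blind tau PET finding ("Given that no treatment effect was observed on" that measure), so a rule written now could be post hoc and would not restore pre-specification.

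**Conclusion.** No change is needed. The stated 80% is correct (80.5% on the protocol's inputs) and names its endpoint. The unstated interval level and joint reading are details that analysts can fill sensibly: report two adjusted differences, each with an 80% interval to match the 0.2, and describe discordant results as they stand. This rests on reading Sections 2.1.1 and 6.4.1 as estimation in a hypothesis-generating study, which their wording and Section 6.9.1 support.

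If the sponsor intended a formal both-required claim, joint power would be about 65% to 76% under equal power and correlation 0 to 0.9, or 56% to 80% with ADCS-ADL power of 70% to 90%, before any covariate gain. Those figures depend on assumed inputs and would not make either estimate wrong. If the sponsor chooses to add a sentence to Section 6.4.1 on the level and the joint reading, it is optional reporting text, to be marked post hoc if double-blind clinical results were already known.

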6.2 SUMMARIES OF CONDUCT OF STUDY

The number of patients who enroll, discontinue (early discontinuation of treatment or early termination from the study), complete the double-blind treatment period (through Week 49 for Cohort 1 *or* Week 61 for Cohort 2), and continue into the OLE will be tabulated by treatment group. Reasons for early discontinuation of treatment or early termination from the study will be listed and summarized by treatment group. Any eligibility criteria exceptions and other major protocol deviations will also be summarized by treatment group.

6.3 SUMMARIES OF TREATMENT GROUP COMPARABILITY

Demographic and baseline characteristics such as age, sex, race, *ApoE4* status, and baseline MMSE score will be summarized with means, standard deviations, medians, and ranges for continuous variables and with frequencies and proportions for categorical variables, as appropriate. Summaries will be presented by treatment arm and overall.

6.4 EFFICACY ANALYSES

6.4.1 Primary Efficacy Endpoints

The co-primary efficacy endpoints are change in ADAS-Cog11 and ADCS-ADL scores from baseline to the last visit of the double-blind treatment period (Week 49 for Cohort 1 *or* Week 61 for Cohort 2). The difference in mean change from baseline to the last visit of the double-blind treatment period between MTAU9937A- and placebo-treated patients will be estimated using an analysis of covariance model adjusting for *ApoE4* status (*ApoE4+* vs. *ApoE4-*), screening MMSE (16–18 vs. 19–21), baseline [¹⁸F]GTP1 PET standard uptake value ratio, age, baseline ADAS-Cog11 or ADCS-ADL scores, and if appropriate, the number of missed study drug infusions during the double-blind treatment period due to the COVID-19 pandemic. Confidence intervals, as well as least squares estimates, will be used to aid in interpretation of study results.

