Patients will be randomly assigned to receive MTAU9937A (4500 mg) or placebo administered by IV infusion in a 1:1 ratio. All patients participating in the OLE will receive MTAU9937A 4500 mg IV infusion. Because both *APOE* genotype and baseline cognitive performance may be associated with subsequent rates of clinical progression, randomization will be stratified by both *APOE* status (*ApoE4*+ vs. *ApoE4*-) and screening MMSE scores (16–18 vs. 19–21).

Patients will be selected on the basis of clinical diagnosis of probable AD dementia. Clinical diagnosis for each patient must be supported by information provided on a Diagnostic Verification Form (DVF), which must be reviewed and approved by the Sponsor or Sponsor delegate.

Eligible patients must be 50–85 years old at the beginning of screening, meet diagnostic criteria for probable AD dementia, and have evidence of cerebral amyloidosis as indicated by CSF analysis (i.e., CSF-enrolled patients) or positive amyloid PET scan by qualitative read (i.e., PET-enrolled patients). The choice between CSF versus PET for determination of cerebral amyloidosis should be made on the basis of the capability of an individual site and/or the preference of an individual patient. If a patient is amyloid negative based on one of the two modalities (CSF assessment or amyloid PET), then the patient may undergo assessment with the other modality during screening; amyloid positivity by either modality is sufficient for eligibility.

At the time of screening, patients must have a MMSE score between 16 and 21 (inclusive) and a Clinical Dementia Rating–Global Score (CDR-GS) of 1 or 2. Patients will be eligible for the study regardless of whether they are receiving standard-of-care symptomatic medications for AD (e.g., cholinesterase inhibitors, memantine, and/or the medical food supplement Souvenaid®). These medications must have been stable for ≥ 2 months prior to screening, and there should be no a priori planned initiation, discontinuation, or dose changes for these medications during the study (double-blind treatment and OLE treatment periods). However, following the initiation of study drug, standard-of-care symptomatic medications for AD may be initiated, dose adjusted, or discontinued as deemed clinically appropriate.

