4.5.7.1 Mini-Mental State Examination

The MMSE is a brief clinical cognitive examination commonly used to screen for dementia and other cognitive deficits (Folstein et al. 1975) that has a total score of 0–30. The MMSE will be administered to patients at screening to determine eligibility for the trial, at baseline, and at other postbaseline timepoints.

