4.5.7.4 Alzheimer’s Disease Cooperative Study—Activities of Daily Living Inventory

The ADCS-ADL (Galasko et al. 1997) is the most widely scale for assessing functional outcomes in patients with AD (Vellas et al. 2008). The ADCS-ADL is administered to caregivers and covers both basic activities of daily living (ADL) (e.g., eating and toileting) and more complex ADL or instrumental ADL (e.g., using the telephone, managing finances, preparing a meal). Scores range from 0 to 78, with higher scores indicating better ADL function.

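### Each co-primary ANCOVA adjusts for its own scale's baseline only, with MMSE in two categories; adding the other scale's baseline is an optional, small efficiency gain, not the repair of a bias.

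*Combined protocol and SAP*

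**What the plan says.** Section 6.4.1 states that the treatment difference in mean change "will be estimated using an analysis of covariance model adjusting for" a fixed list. The list is ApoE4 status, "screening MMSE (16–18 vs. 19–21" (a two-level factor that is also a randomisation stratum), baseline tau PET SUVR, "age, baseline ADAS-Cog11 or ADCS-ADL scores" and, if appropriate, the number of infusions missed because of COVID-19. The synopsis gives the same list. Section 6.4.2 analyses CDR-SB and MMSE in the same way as the primary endpoints and does not say which baseline score enters.

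The synopsis justifies stratification partly on the ground that "baseline cognitive performance may be associated with subsequent rates of clinical progression"; Section 3.1.1 repeats this.

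The finer baseline data exist. Section 4.5.7.1 says: "The MMSE will be administered to patients at screening to determine eligibility for the trial, at baseline, and at other postbaseline timepoints". Section 4.5.7.4 describes ADCS-ADL thus: "Scores range from 0 to 78, with higher scores indicating better ADL function". Appendices 1 and 3 schedule ADAS-Cog11, ADCS-ADL, MMSE and CDR at both screening and baseline, and require the baseline ratings before the first dose.

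**The concern.** The word *or* gives each model one continuous clinical baseline. In the ADCS-ADL model, cognition is represented clinically only by an MMSE cut between 18 and 19 within a six-point eligibility range. In the ADAS-Cog11 model, function is not represented at all. The documents give no reason for leaving out the other scale's baseline.

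If those baselines predict change beyond the covariates already listed, that information stays in the residual variance and the intervals for the co-primary endpoints are somewhat wider than necessary. Chance imbalance between arms in function, or in cognition within an MMSE stratum, would also go unadjusted. The validity of the comparison is not at stake.

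**Working it through.** **Inputs from Section 6.1.** "This study will enroll approximately 260 patients", with an "IV placebo dose arm in a 1:1 ratio"; placebo decline 6 points; 35% relative reduction; SD 7.5; dropout 10%; two-sided alpha 0.2; power about 80%.

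**Reproducing the plan's figure.**
- Difference: 0.35 × 6 = 2.1 points.
- Evaluable per arm: 260 × 0.9 / 2 = 117.
- Standard error: 7.5 × √(2/117) = 0.981.
- Power: Φ(2.1/0.981 − 1.282) = Φ(0.860) = 80.5% (80.4% with the noncentral t).
- In reverse, 80% power needs 2 × (1.282 + 0.842)² × 7.5² / 2.1² = 115 per arm. Then 115/0.9 rounds up to 128 per arm, 256 in total, against about 260 stated. The design reproduces.

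**Effect of extra baselines on ADAS-Cog11.** Let q be the share of residual variance that the added baselines explain. The documents give no value, so q is an assumption. The SD becomes 7.5 × √(1 − q), with 7.5 treated as the residual SD of the planned model. The 80% CI half-width is 1.282 × SD × √(2/117). The last column is 234 × [1/(1 − q) − 1].

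| q (assumed) | SD | Power | 80% CI half-width | Equivalent extra evaluable patients |
|---|---|---|---|---|
| 0 | 7.50 | 80.5% | 1.26 | 0 |
| 1% | 7.46 | 80.8% | 1.25 | about 2 |
| 3% | 7.39 | 81.4% | 1.24 | about 7 |
| 5% | 7.31 | 82.0% | 1.22 | about 12 |

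The largest reduction in half-width over this range is 1.257 − 1.225, about 0.03 points. If q were 10%, power would be 83.5%; nothing in the documents supports a value that high.

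**Cost of a useless covariate.** The planned model has 7 parameters (intercept, treatment and five covariates, leaving out missed infusions), so 234 − 7 = 227 residual degrees of freedom. An uninformative covariate inflates the variance of the treatment difference by roughly 1/227 = 0.4%. At q = 1% from one added covariate, a little under half of the tabulated gain is therefore given back.

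**The two-category MMSE.** Assume scores uniform on 16 to 21. The variance is 35/12 = 2.92. The two groups have means 17 and 20 around 18.5, so the between-group variance is 1.5² = 2.25. The split keeps 2.25/2.92 = 77% of the linear information. If MMSE correlates ρ with change, replacing the split by the score adds a partial R² of ρ²(1 − 0.771)/(1 − 0.771ρ²): 0.009 at ρ = 0.2 and 0.042 at ρ = 0.4 (ρ is also assumed). This ignores overlap with the other covariates, so it is more likely too high than too low. Dichotomising costs little by itself.

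**ADCS-ADL.** Section 6.1 gives no SD, effect or correlation for this scale, so no equivalent table can be made.

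**The case against.** The strongest reply is that this is a preference rather than a defect. Both models already carry the two stratification factors, the endpoint's own continuous baseline, age and continuous tau PET SUVR. The sentence about baseline cognition justifies stratification, and the model does adjust for the strata. A half-width change of at most 0.03 points would not alter the reading of a hypothesis-generating phase II trial at two-sided alpha 0.2. This stands, and it limits the point to an optional improvement.

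Two further objections concern the size and also stand. First, Section 6.1 gives 7.5 as an SD across patients, not as a residual SD. If the planned covariates already explained 10–20% of variance (assumed), base power would be 83.5–86.7%, and a further 5% would add about 1.3–1.4 points instead of 1.5. Second, any gain requires the added baselines to be prognostic beyond the existing list, which the documents do not show.

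Timing is a fair worry too. Section 6.9.1 permits up to two unblinded sponsor efficacy analyses. Section 5.1.1.2 refers to unblinded safety data from this study. The Version 5 amendment rationale mentions that no tau PET effect was observed in the double-blind period, without naming the study. None of this establishes that an unblinded efficacy look at the co-primary scales has taken place, but a covariate change made after one would be open to criticism as post hoc. The Data Analysis Plan mentioned in Section 6.5 is not available, so whether it adds covariates cannot be checked.

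What survives is that the baselines are already scheduled, no reason is given for omitting them, and using them costs almost nothing.

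**Conclusion.** The covariate list is as described, and extending it is a reasonable optional efficiency step. On the stated assumptions (7.5 as residual SD, 117 evaluable per arm, added baselines explaining 1–5% of residual variance), ADAS-Cog11 power moves from 80.5% to about 80.8–82.0%. With no added prognostic value there is no gain, only a slight loss of degrees of freedom.

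A reader might infer three stronger things that the documents do not support:
- *That the estimates are biased or the primary model is wrong.* Omitting a prognostic covariate from a randomised comparison of means does not bias the treatment difference, and the model is analysable as written.
- *That the intervals are certainly wider than they need be.* This depends on a correlation that appears nowhere in the documents.
- *That ADCS-ADL would gain more because its model lacks a continuous cognitive score.* This is plausible but cannot be computed, and that model does carry continuous tau PET SUVR.

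**What to change.** In Section 6.4.1 and the synopsis, replace *or* by *and*, so that baseline ADAS-Cog11 and baseline ADCS-ADL both enter both co-primary models. Keep ApoE4 status and the two-category MMSE as stratification factors. Optionally add continuous baseline MMSE to the ADCS-ADL model. In Section 6.4.2, state that CDR-SB and MMSE each use their own baseline plus these two scores.

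Specify simple imputation, such as the overall mean, for a missing baseline covariate. Otherwise a patient lacking one scale's baseline would drop out of the other scale's model.

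Fix the list before any unblinded efficacy look and document the date. If such a look has already occurred, keep the stated model as primary and report the expanded model as supportive.

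The cost is a few lines of wording and 2–3 degrees of freedom across the two co-primary models: one for ADAS-Cog11, and one or two for ADCS-ADL. No new data, visits or patients are needed.
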